3.3.4.3 Discontinuation of the trial by the sponsor

BI reserves the right to discontinue the trial overall or at a particular trial site at any time for the following reasons:

1. Failure to meet expected enrollment goals overall or at a particular trial site.
2. New efficacy or safety information invalidating the earlier positive benefit-risk-assessment.
3. Deviations from Good Clinical Practice (GCP), the trial protocol, or the contract impairing the appropriate conduct of the trial.

Clinical Trial Protocol

Proprietary confidential information © 2025 Boehringer Ingelheim International GmbH or one or more of its affiliated companies

The investigator / the trial site will be reimbursed for reasonable expenses incurred in case of trial termination (except in case of the third reason).

Clinical Trial Protocol

Proprietary confidential information © 2025 Boehringer Ingelheim International GmbH or one or more of its affiliated companies

4. TREATMENTS

4.1 INVESTIGATIONAL TREATMENTS

The BI investigational products are provided by Boehringer Ingelheim Pharma GmbH & Co. KG.

4.1.1 Identity of the Investigational Medicinal Products

Table 4.1.1: 1 Test product 1

Substance:	BI 764198
Pharmaceutical formulation:	Capsule
Unit strength:	20 mg, 40 mg, and 80 mg
Posology:	q.d.
Mode of administration:	Oral (p.o.)

Table 4.1.1: 2 Test product 2

Substance:	Placebo to match BI 764198
Pharmaceutical formulation:	Capsule
Unit strength:	Not applicable
Posology:	q.d.
Mode of administration:	Oral (p.o.)

4.1.2 Selection of doses in the trial

The proposed doses in this study, 20 mg, 40 mg, and 80 mg were chosen based on acceptable Phase 1 clinical trial safety data generated with 80 mg for up to 14 days of daily dosing in healthy volunteers and safety margins based on nonclinical toxicological findings (████████).

Clinical Trial Protocol

Proprietary confidential information © 2025 Boehringer Ingelheim International GmbH or one or more of its affiliated companies

The human therapeutic dose in patients with CKD has been estimated based on plasma exposures demonstrating efficacy in a mouse unilateral ureteral obstruction model in which BI 764198 levels above the mouse manual patch-clamp IC₉₀ value (after correcting for plasma protein binding) produced a significant pharmacological effect. Coverage of the human manual patch-clamp IC₉₀ value of 212 nM (equivalent to 77 nM unbound, considering an unbound fraction of 36.4% in human plasma (██████)) is predicted to be required in patients to provide therapeutic benefit. The conservative assumption is that the C_{trough,ss} value needs to be above the IC₉₀ value.

In the multiple rising dose (MRD) study (██████), the gMean (gCV%) C_{trough,ss} values of dose groups 20 mg, 40 mg and 80 mg were 164 nM (28.6), 351 nM (20.2) and 731 nM (29.1), respectively. Patients with primary FSGS likely have slightly higher exposures due to their impaired renal function relative to healthy subjects (see [section 1.2](#)). Simulations for patients with an eGFR of 60 mL/min/1.73 m² were performed based on a population PK analysis including studies 1434-0001 (██████), 1434-0002 (██████), and 1434-0007 (██████). The predicted median C_{trough,ss} (95% prediction interval) of dose groups 20 mg, 40 mg and 80 mg were 221 nM (134 - 356 nM), 432 nM (264 - 710 nM) and 867 nM (529 - 1381 nM), respectively.

Thus, the therapeutic dose of BI 764198 is estimated to be between 20 and 40 mg. However, in the absence of the possibility to assess target engagement in humans and given the uncertainty of a demonstrable pharmacodynamic effect solely based on in vitro dose estimation, a higher exposure (at multiples of IC₉₀) may be needed to observe a therapeutic response *in vivo*.

From an efficacy perspective, in this mechanistic study, we intend to investigate high doses of BI 764198 (above the anticipated therapeutic dose) in order to explore whether TRPC6 inhibition induces a clinically meaningful UPCR response in patients with primary or TRPC6 monogenic FSGS. Beyond the establishment of the proof of clinical principle, which is a key objective in this trial, future studies, including a dedicated Phase 2 dose finding trial will enable a thorough investigation of therapeutic doses and the establishment of the minimum effective dose.

4.1.3 Method of assigning patients to treatment groups

After the assessment of all inclusion and exclusion criteria, each eligible patient will be randomized to one of the treatment groups according to the randomization plan in a 1:1:1:1 ratio via Interactive Response Technology (IRT). Randomization will be stratified by use of corticosteroids.

Note that the trial medication number is different from the patient number (the latter is generated during screening via the IRT System). A total of 60 patients will be randomized with approximately 15 patients in each treatment group. Patients randomized by error and did not receive any trial medication may be replaced.

Clinical Trial Protocol

Proprietary confidential information © 2025 Boehringer Ingelheim International GmbH or one or more of its affiliated companies

4.1.4 Drug assignment and administration of doses for each patient

Table [4.1.4: 1](#) shows the trial medication schedule for each treatment group.

Table 4.1.4: 1 BI 764198 and placebo treatments

Dose group	Substance	Pharmaceutical form	Unit strength	Number of capsules per administration	Total daily dose
1	BI 764198	Capsule	20 mg	1 capsule q.d. for 12 weeks	20 mg
2	BI 764198	Capsule	40 mg	1 capsule q.d. for 12 weeks	40 mg
3	BI 764198	Capsule	80 mg	1 capsule q.d. for 12 weeks	80 mg
1-3	Placebo*	Capsule	--	Matching placebo for 12 weeks	--

* Subjects receiving placebo are equally distributed across all three treatment groups.

After eligibility of the patient is confirmed during the screening period, patient will be randomized in the IRT Platform at least 7 days before the scheduled visit 2 date. Randomization will initiate the direct shipment of trial medication to the patient. Each patient will receive trial medication from an external depot contracted by the sponsor. Patient's name and address will not be made available to the sponsor. Patient will receive sufficient trial medication for the entire 12-week duration of the treatment period.

Prior to shipment of the trial medication, study site staff will train the patient on handling, storage, and use of the trial medication. Site staff should contact the patient by telephone (video call if possible) in about 24 hours (or next working day) after the site receives the delivery notification from the courier. During this contact, the site should remind the patient of the proper storage requirements for the medication. The patient should also be instructed not to open the trial medication package and to bring all the medication to the clinic for visit 2.

Medication from one of the bottles will be used to dose the patient at visit 2. Site staff will inspect the shipment to ensure patient has received all the medication. All trial medication (except the capsule used for dosing at visit 2) will be returned to the patient with instructions for administration of medication at home.

- Patient will self-administer the trial medication at home. On study visit days, patient must receive the dose during the study visit (at the clinic or at home) after the pre-dose PK sample is taken.
- Patients should take one capsule a day with or without food, preferably at the same time of the day in the mornings.
- In case dosing occurs before 18:00 hours (6 p.m.), the next dose should be in the morning the next day (followed by morning dosing thereafter).
- In case dosing occurs before midnight, the next dose should be at about noon the next day (followed by morning dosing thereafter).
- If dosing does not occur on a particular day (not taken until midnight), the next dose should be in the morning the next day (followed by morning dosing thereafter).

Clinical Trial Protocol

Proprietary confidential information © 2025 Boehringer Ingelheim International GmbH or one or more of its affiliated companies

The route of administration is by mouth (p.o.). Trial treatment may be restarted after temporary discontinuation (section [3.3.4.1](#)). Dose reduction or increase are not allowed.

On study visit days, trial medication will be administered at the specified time (see Table [10.1: 1](#)). Patient should be instructed to bring all used and unused bottles to the clinic for each study visit. Site staff will inspect all the trial medication and also calculate compliance (section [4.3](#)) by capsule count. Site will destroy the empty bottles with documentation and re-dispense the remaining medication to the patient at each study visit. At the EoT visit all remaining used and unused bottles with trial medication will be collected from the patient. Study visits should be rescheduled if trial medication is not available for dosing the patient after the pre-dose PK sample is drawn.

If local regulations or site procedures or if the patient does not permit shipment of the trial medication directly to the patient, medication can be shipped to the study site. Randomization will still be completed at least 7 days before the scheduled visit 2 date to initiate trial medication shipment to the site. Site staff will dispense the trial medication to the patient. For storage conditions, see section [4.1.7](#).

Unscheduled supply of trial medication can be initiated by the study site in the IRT. Patient should contact the site if a need for additional medication supply arises.

A paper diary will be dispensed and collected at time points shown in the [Flow Chart A](#). Patient will record the date and time of trial medication intake in the diary on the 3 days before EoT visit, and on the previous day for all other visits. Patients should be instructed to bring the completed diary for review by the site staff. Date and time of medication intake for the 3 days prior to EoT as well as the previous day for all other visits will be entered in the eCRF. Date and time of medication intake during the study visit will also be entered in the eCRF. A copy of the paper diary will be placed in the ISF.

For patients participating in the trial remotely via the DCT model, the MRN will visit the patient's home for the study visit and complete the trial procedures including inspection of the trial medication, providing instructions for administration of medication at home, administering trial medication at the specified time during the study visit, and review of the paper diary. Additional guidance on remote study visits will be provided in a separate DCT operational manual which will include instructions for handling used empty bottles and unused trial medication.

COVID-19 pandemic - contingency plan:

During the COVID-19 pandemic physical visits to the sites (for patients not participating in the DCT model) may need to be restricted to ensure patient safety. Based on a thorough assessment of the benefits and risks, the investigator may still decide to continue the trial treatment, after discussion with the sponsor.

Clinical Trial Protocol

Proprietary confidential information © 2025 Boehringer Ingelheim International GmbH or one or more of its affiliated companies

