24. A medication diary (paper) will be dispensed to the patient. Patient should record the date and time of medication intake at home for the 3 days prior to EoT, and for the previous day for all other clinic visits. Patients should bring the diary to the clinic for review. For more information, see section 4.1.4. If possible, a few days before the visit patients should be reminded (e.g., via telephone) to complete the medication diary, and to not take the study drug on the day of the study visit.
25. Patient will bring all the trial medication received directly from the central depot to the clinic for visit 2 (first dosing visit). Site will inspect all the trial medication and provide instruction to the patient on how medication is administered at home and how the medication should be brought to the clinic visits. Site will open the first bottle to administer the first dose in the clinic. When the patient is contacted after the trial medication is delivered to the patient's home (see footnote 23), they should be reminded to bring the trial medication to the clinic for visit 2. If possible, patients should be reminded (e.g. by telephone) to bring

Clinical Trial Protocol

Proprietary confidential information © 2025 Boehringer Ingelheim International GmbH or one or more of its affiliated companies

the trial medication to the clinic before each visit. Study visits will have to be rescheduled if trial medication is not available during the applicable visits. For information on how trial medication will be handled during the course of the trial, see section 4.1.4.

26. A separate eCRF will be used to collect specific data related to acute kidney injury (section [3.3.4.1](#)). After the FUP1 visit until the individual patient's end of trial only cancers of new histology and exacerbations of existing cancer, all trial drug related SAEs and all trial drug related AESIs will be collected (section [5.2.6.2.1](#)).
27. Medication compliance (section [4.3](#)) will be checked by capsule count by study site staff. For information on medication return, see [section 4.1.4](#).

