1.2 DRUG PROFILE

BI 764198 is an oral, small-molecule inhibitor of TRPC6. It is being developed for the treatment of advanced chronic kidney disease on top of standard of care.

Mode of action:

BI 764198 is a potent inhibitor of human TRPC6 (IC_{50} : 14.4 nM; IC_{90} : 77 nM), rat TRPC6 (IC_{50} : 12.9 nM), mouse TRPC6 (IC_{50} : 19.3 nM), dog TRPC6 (IC_{50} : 44.2 nM) and cynomolgus monkey TRPC6 (IC_{50} : 10.0 nM) in *in vitro* manual patch clamp assays using human HEK293 cells with inducible TRPC6 expression.

Key pharmacokinetic characteristics:

Following administration of single and multiple doses ranging from 1 mg to 240 mg in humans, BI 764198 was rapidly absorbed into the systemic circulation with maximum plasma concentrations occurring in the range of 0.75 h to 2 h post-dose time to maximum plasma concentration (t_{max}). BI 764198 was cleared from plasma with an apparent $t_{1/2}$ ranging from 12.7 h to 17.4 h, independent of the dose. At doses of 10 mg or higher, the exposure of BI 764198 was linear. After multiple dose administration, steady state AUC and C_{max} values increased linearly between 20 mg and 80 mg doses and BI 764198 shows time independent PK up to 80 mg. A steady state was achieved by 3-4 days with modest accumulation based on AUC_{0-24h} , (1.33-1.48) and C_{max} (1.13-1.43). The fraction of BI 764198 excreted unchanged in urine over 48 h was between 14% and 30% after single dose administration and 21% to 29% over 24 h after multiple dose administration. In study 1434-0002 [REDACTED], in otherwise healthy participants who had renal impairment, gMean BI 764198 AUC increased by 48% (moderate impairment) and 78% (severe impairment) and C_{max} increased by 14% (moderate renal impairment) and 12% (severe renal impairment) after a single dose of 40 mg compared with healthy controls.

Clinical Trial Protocol

Proprietary confidential information © 2025 Boehringer Ingelheim International GmbH or one or more of its affiliated companies

After multiple doses of BI 764198 (up to 160 mg), gMeans for $AUC_{t,ss}$ and $C_{max,ss}$ were higher by 3-36% and 21-47% respectively, when comparing Japanese (1434-0003) and Caucasian (1434-0007) data. This may be related to the lower body weight in Japanese subjects (mean weight 63.25 kg vs. 78.08 kg in Caucasian).

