BI 764198 is not expected to lead to a clinically relevant reduction in the exposure of oral contraceptives due to an increased metabolism via enzyme induction (████████). BI 764198 (80 mg once daily over 10 days) did not change the pharmacokinetics of the sensitive CYP3A4 substrate midazolam. Thus, BI 764198 is not considered to be a CYP3A4 inducer *in vivo*. From *in vitro* studies using human hepatocytes, there is no indication that BI 764198 activates other nuclear receptors (AHR or CAR) that trigger induction of other drug metabolizing enzymes involved in metabolism of oral contraceptive components, such as UGTs and sulfotransferases (SULTs).

Residual Effect Period

Clinical Trial Protocol

Proprietary confidential information © 2025 Boehringer Ingelheim International GmbH or one or more of its affiliated companies

The Residual Effect Period (REP) of BI 764198 is 119 hours, i.e. 5 days, based on 5 times 23.8 hours, the maximum value for $t_{1/2}$ in patients with moderate renal impairment [REDACTED]. This is the period after the last dose with measurable drug levels and/or pharmacodynamic effects still likely to be present.

Data from toxicology studies

The toxicity profile of BI 764198 has been assessed in a comprehensive set of safety pharmacology studies, genetic toxicology and phototoxicity studies, repeat dose general toxicology studies (up to a duration of 26 weeks in the rat and 39 weeks in the dog) embryo-foetal development toxicity studies (rat and rabbit), and a fertility and early embryonic development study (in rat). BI 764198 has been well tolerated at clinically relevant plasma exposures in toxicity studies. Exposure multiples were calculated based on the human estimated steady state C_{max} of 3650 nM and AUC_{0-24hr} of 40200 nM•h for a dose of 80 mg once daily.

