2.1.3 Secondary endpoints

[figure not shown]
The secondary endpoints are:

- Change in 24-hour UPCR relative to visit 3 at week 12
- Change in 24-hour UPCR relative to baseline at week 13
- Change in 24-hour urinary protein excretion relative to baseline at week 12
- The following pharmacokinetic parameters of BI 764198 will be determined if feasible:
 - Steady state trough concentration $C_{pre,ss}$ on week 4 and week 12

For details on efficacy assessments and definition of baseline, see section [5.1.1](#).

[figure not shown]
Clinical Trial Protocol

Proprietary confidential information © 2025 Boehringer Ingelheim International GmbH or one or more of its affiliated companies

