5.2.2 Secondary endpoint(s)

[figure not shown]
Secondary endpoint(s) will be used as described in the CTP, Section 2.1.3 and assessments described in CTP, Section 5.1.1.

[figure not shown]
The secondary endpoints are:

Secondary endpoints are listed in CTP Section 2.1.3 and will be assessed, as follows:

- Change in 24-hr UPCR relative to visit 3 at week 12: the samples will be from the 24-hour urine samples collected at visits 3 and 12.
- Change in 24-hr UPCR relative to baseline at week 13: the samples will be the 24-hour urine samples collected at baseline and week 13.
- Change in 24-hour urinary protein excretion relative to baseline at week 12.
- The following pharmacokinetic parameters of BI 764198 will be determined, if feasible:
 - Steady state trough concentration $C_{pre,ss}$ on week 4 and week 12

For details on efficacy assessments and definition of baseline, see CTP Section 5.1.1.

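### Dose times are recorded for three days before EoT but only one day before week 4, so a dose missed two days before the week-4 trough sample cannot be dated, although the steady-state trough is a secondary endpoint at both visits

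*Protocol*

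**What the plan says.** SAP 5.2.2 lists "Steady state trough concentration" (Cpre,ss) as a secondary endpoint, and Protocol 2.1.3 fixes its timing: "on week 4 and week 12". Week 4 is visit 4 (day 29) and week 12 is the EoT visit (day 85). Both have a pre-dose PK sample (Protocol Table 10.1: 1).

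Under Protocol 4.1.4 the patient records dose date and time "in the diary on the 3 days before EoT visit, and on the previous day for all other visits". The same split governs which home dose times are transferred to the eCRF. Flow Chart A footnote 24 repeats the diary rule.

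On adherence more broadly, Protocol 4.1.4, Protocol 4.3 and Flow Chart A footnote 27 have site staff count capsules and calculate compliance at visits. SAP 7.3 says that neither counts nor compliance percentages are collected and plans only a by-patient listing of non-compliance.

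Protocol 7.2.1 and SAP 6.4 keep a PK endpoint out of the PK analysis set if a PK-relevant protocol violation or non-evaluability applies.

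**The concern.** One endpoint is checked against two standards. Protocol 1.2 says steady state takes 3-4 days to reach, so a trough reflects more than the last dose. Before EoT, the dose record covers most of the period that matters. Before week 4 it covers only the day before.

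A capsule count can show that a dose was missed since visit 3, but not on which day, and a late dose leaves no trace in a count. The PK-set exclusion therefore cannot be applied on this ground at week 4 in the way it can at EoT. An affected trough would be summarised as a steady-state value. Protocol 5.3.1 also sends these samples to population PK and PK/PD analyses, where an undated dosing gap could be taken for pharmacokinetic variability.

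**Working it through.** The documents give no figure for the effect of a missed dose, so there is none to reproduce. The check uses superposition with mono-exponential decline.

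**Inputs**
- Dosing interval 24 h (Protocol 4.1.4: "Patients should take one capsule a day with or without food, preferably at the same time of the day in the mornings").
- Half-life in phase 1: "ranging from 12.7 h to 17.4 h, independent of the dose" (Protocol 1.2).
- Longest half-life, in moderate renal impairment: 23.8 h. It underlies the residual effect period, "based on 5 times 23.8 hours" (Protocol 1.2). Patients with eGFR down to 30 are eligible, so it is relevant here.
- Accumulation on AUC over 24 h: 1.33-1.48 (Protocol 1.2).
- Between-subject gCV of trough: 20.2-29.1% (Protocol 4.1.2).
- About 15 patients per arm (Protocol 4.1.3).

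**Check on the plan's own PK figures.** 5 × 23.8 h = 119 h, which matches the stated residual effect period. With r = 2^(−24/t½), accumulation is 1/(1−r): 1.37 at 12.7 h and 1.62 at 17.4 h, against 1.33-1.48 stated. The low end agrees within 3%; the high end is about 10% above. The loss is therefore also computed from the stated accumulation.

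**Loss in one patient's trough.** The steady-state trough is proportional to r + r² + … = r/(1−r). A dose missed k days before the sample removes r^k, a relative loss of r^(k−1)(1−r).

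| t½ | r | k=1 | k=2 | k=3 | k=4 |
|---|---|---|---|---|---|
| 12.7 h | 0.270 | 73.0% | 19.7% | 5.3% | 1.4% |
| 17.4 h | 0.384 | 61.6% | 23.7% | 9.1% | 3.5% |
| 23.8 h | 0.497 | 50.3% | 25.0% | 12.4% | 6.2% |

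From the stated accumulation, r = 1 − 1/1.33 = 0.248 and 1 − 1/1.48 = 0.324. The k=2 loss is then 0.248 × 0.752 = 18.7% and 0.324 × 0.676 = 21.9%. Together the k=2 range is about 19-25%.

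**What each diary window leaves undated.** At week 4 the k=1 dose is recorded, so the largest undated single miss is k=2: 19.7-25.0%. At EoT, k=1 to 3 are recorded, so it is k=4: 1.4-6.2%. A 3-day record before visit 4 would bring week 4 to the EoT figure.

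**Effect on the arm summary.** If m of 15 patients miss the k=2 dose with loss L, the geometric mean falls by 1 − (1−L)^(m/15). For L = 19.7-25.0%, m = 1 gives 1.5-1.9% and m = 3 gives 4.3-5.6%. The values of m are assumptions; the documents give no frequency of missed doses.

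**The case against.** The case for leaving the diary alone has real content.

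- **A reader might infer that the miss goes undetected.** It need not. Bottles come back at each visit and capsules are counted, so a surplus can appear at visit 4. What is lost is the date. SAP 7.3 leaves it unclear whether the count reaches the analysis data at all.
- **A reader might infer that the endpoint is biased by 20-25%.** The documents do not support that. The figure is the error in one patient's trough, and the arm-level shift cannot be sized without a frequency of misses.
- **The worst case is already covered.** A dose missed the day before costs 50-73% and is recorded at both visits. The last two doses supply 1 − r², about 93%, 85% and 75% of the trough at the three half-lives.
- **A reader might infer that patients would be pushed below the IC90.** At 20 mg the predicted median of 221 nM would fall to about 166-177 nM, against 212 nM. But the 95% prediction interval in Protocol 4.1.2 (134-356 nM) already spans 212 nM, and the phase 1 geometric mean was 164 nM. At 40 and 80 mg a 25% loss leaves about 324 and 650 nM. No trough-versus-IC90 classification appears in the visible plan.
- **No week-4 versus week-12 comparison is specified.** SAP 7.5.2 plans descriptive statistics and figures only.
- **The window was chosen on purpose.** The 25 October 2022 amendment moved serial PK sampling to EoT only, to reduce patient burden, and aligned the diary with that schedule.
- **A detailed evaluability rule may exist in text not shown.** Its absence cannot be claimed.

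These points limit the size of the problem. They do not remove it: the serial-PK rationale explains the longer window at EoT but does not address the week-4 trough, which remains a secondary endpoint. Any evaluability rule, wherever it is written, needs dose dates that are not collected before visit 4.

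**Conclusion.** The point holds as a low-severity gap in data collection. A dose missed two days before the week-4 sample cannot be dated from the diary or eCRF and would lower that patient's trough by about 19-25%, similar in size to the stated between-subject gCV. A dose missed three days before is equally undated and costs 5-12%. On the geometric mean of an arm of 15 the k=2 effect is about 1.5-1.9% per affected patient.

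This rests on mono-exponential decline, regular 24-hour dosing otherwise, and the half-lives in Protocol 1.2. The 25% end uses the longest half-life reported in moderate renal impairment. The number of affected patients is unknown. Nothing here touches the primary endpoint or any planned test.

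**What to change.** 1. In Protocol 4.1.4 and Flow Chart A footnote 24, require dose date and time for the 3 days before visit 4, as before EoT, with the same eCRF entry.
2. Apply the existing PK-set non-evaluability exclusion (Protocol 7.2.1, SAP 6.4) in the same way to week-4 and week-12 troughs when a dose in that 3-day window was missed.
3. Reconcile Protocol 4.1.4 and 4.3 with SAP 7.3, so that it is clear whether capsule counts reach the trial data.

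The cost is two more diary lines and matching eCRF fields per patient at one visit. Footnote 24 already provides for a reminder a few days before visits. A few week-4 troughs may drop out of the steady-state summary.
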